## Study Summary

Title	Placebo-controlled trial of bupropion for smoking cessation in pregnant women
Short Title	Bupropion Study
Protocol Number	820364
Phase	Phase II
Methodology	This is a prospective, placebo-controlled RCT of the efficacy and safety of bupropion in combination with behavioral counseling for smoking cessation during pregnancy. Pregnant smokers (N=360) will receive bupropion or placebo treatment for 10 weeks, under strict double-blind conditions.
Study Duration	Approximately 54 months
Study Center(s)	Multicenter study: University of Pennsylvania (Penn): Dickens Women's Health Center (DWHC) at the Hospital of the University of Pennsylvania (HUP) and Pennsylvania Hospital (PAH) Thomas Jefferson University: Jefferson University Department of Obstetrics and Gynecology Associates (JOGA) and Maternal Addiction, Treatment, Education and Research Center (MATER; Jefferson) and Christiana Care Hospital System, Newark, DE.
Objectives	
Specific Aim 1: Conduct a 10-week placebo-controlled trial of bupropion 300 mg/day in 360 pregnant smokers who are at 13–26 weeks gestation. We will monitor smoking behavior and adverse effects (AEs) of the medication during a 10-week treatment period. A post-treatment follow-up visit will be held at 24 weeks post target quit date (post-TQD). We will also provide two booster counseling sessions at weeks 2 and 6 postpartum and a final research evaluation at 24 weeks post-TQD. We will use text messages to send pregnancy-relevant information and medication-adherence cues to improve medication adherence. In addition to examining the effect of treatment on smoking cessation, we will monitor its effects on pregnancy outcomes (length of gestation, rate of pregnancy complications, and birth outcomes).
 
Specific Aim 2: Assess changes in depression symptoms and craving as mediators of bupropion's effect on quit rates.
 
Exploratory Aim: Explore genetic, metabolic, and social/behavioral moderators of the efficacy of bupropion on cigarette abstinence and safety. To generate new hypotheses, we will explore whether the risk of AEs and the efficacy of bupropion treatment (vs. placebo) are moderated by: 1) the rate of nicotine metabolism (i.e., nicotine metabolite ratio (NMR)) and variation in CYP2A6; 2) variation in CYP2B6 and plasma concentrations of bupropion and hydroxybupropion; and 3) variation in social/behavioral variables, including weight concerns, body image, and the presence of other smokers in the home.

Number of Participants	360
Diagnosis and Main Inclusion Criteria	Pregnant Smokers who are at 13-26 weeks gestation.
Study Product, Dose, Route, Regimen	Bupropion tablets and matching calcium carbonate tablets as placebo for blinding. Maximum bupropion daily dosage is 300 mg by mouth per day. Dosing will be for 3 days at 150 mg per day and then 150 mg twice daily.
Duration of administration	10 weeks

CONFIDENTIAL

This material is the property of the University of Pennsylvania. Do not disclose or use except as authorized in writing by the study sponsor

Reference therapy	placebo
Statistical Methodology	
Preliminary analyses will assess sample characteristics (e.g., age, race, study site) by treatment using t-test or contingency table methods. These variables will also be examined for their relationship to completion of outcome assessments. Variables related to treatment arm or completion of follow ups will be included as covariates in analyses of study aims. Compliance measures will be evaluated across treatment arms, and controlled for in primary analyses. We will use intent-to-treat as the primary method to evaluate study aims. For Aim 1, we will test treatment group differences in a binary abstinence outcome that is a repeated measure using a generalized estimating equations (GEE) model with a logit link. Quit rates after 10 weeks of study medication and at 24 weeks post-TQD will represent our primary outcome variables. Medication group (bupropion vs. placebo) and time point (10 and 24 weeks) will be treated as categorical predictor variables, and the model will predict separate effects of treatment on abstinence at each time point (an interaction). Mean birth weight will be compared for treatment groups using a two-sample t-test, in the context of multiple linear regression. We will also compare treatment arms for equivalence of the frequency of moderate-to-severe adverse events (individual and total). For Aim 2, we will use a regression-based path model approach to examine mediation of treatment effects by changes in depression and craving scores, which will be entered in the model as standardized pre-post differences, continuously distributed and treated as normal in linear regression. The effects of treatment arm on mediators, and of mediators on outcome, will be assessed using linear regression and standardized variables. For Aim 3, we will explore whether the risk of adverse events and the efficacy of bupropion treatment (vs. placebo) is moderated by: 1) the rate of nicotine metabolism and variation in CYP2A6; 2) the rate of bupropion metabolism (i.e., variation in CYP2B6 and plasma concentrations of bupropion and hydroxybupropion); and 3) variation in social/behavioral variables, including weight concerns, body image, and the presence of other smokers in the home.

CONFIDENTIAL

## 1. Introduction

This document is a protocol for a human research study. This study is to be conducted according to US and international standards of Good Clinical Practice (FDA Title 21 part 312 and International Conference on Harmonization guidelines), applicable government regulations and Institutional research policies and procedures.

### 1.1. Background

**Smoking During Pregnancy is a Major US Public Health Problem:** Smoking during pregnancy is a major modifiable cause of poor pregnancy and child health outcomes in the US (1, 2). Maternal smoking increases the risk of a number of serious adverse outcomes of pregnancy, including spontaneous abortion, placental complications, preterm delivery, and fetal and neonatal death. The most consistent adverse effect of smoking during pregnancy is low birth weight (LBW, i.e., <2500 g) (1, 24, 25), the risk of which doubles with maternal smoking (2). In turn, LBW (particularly very low birth weight, i.e., <1500 g), exponentially increases morbidity and mortality risk (3). In the US, maternal smoking is responsible for 30% of LBW babies, 10% of premature deliveries, and 5% of infant deaths (7). Fortunately, smoking cessation by 16 weeks gestation (9, 10), or as late as the third trimester (10), results in a near-normal birth weight infant. Reductions in smoking also increase birth weight (26). Despite these risks, the majority of women who are smoking at the time of their first prenatal visit continue to smoke, risk factors for which include being unmarried, less educated, heavier smokers (>1/2 pack per day), depressed, with partners who smoke (27-30).

#### **Interventions for Smoking Cessation in Pregnant Smokers:**

**Behavioral Interventions for Smoking in Pregnancy:** Smoking cessation efforts in pregnant women have depended largely on behavioral interventions alone, despite consistent evidence that combining behavioral and pharmacologic strategies is more effective than either alone. A meta-analysis of 72 trials (11), including randomized controlled trials (RCTs) in over 20,000 pregnant smokers, showed a modest reduction in smoking by women who received a behavioral intervention relative to usual care [risk ratio (RR) = 0.94]. Babies born to women in the intervention groups were less likely to have a low birth weight (RR = 0.83) and to be born preterm (RR = 0.86). Mean birth weight was 53.9 g (95% CI = 10.44 g to 95.40 g) greater in the intervention groups. A review of the findings from six controlled trials with pregnant smokers of lower socioeconomic status (SES) showed that financial incentives for smoking cessation was efficacious during pregnancy and the early postpartum period, with abstinence rates several-fold those of controls (31). The intervention also improved estimated fetal growth, mean birth weight, and the percentage of low-birth-weight infants. The high cost of the incentives limits the impact of this approach, particularly in public settings with limited funding. Further, there were high relapse rates once the incentives were removed.

Behavioral interventions for smoking among pregnant women are limited by several other factors. First, they are least effective in heavier smokers, with a quit rate of 20% in pregnant women who smoke <10 cigarettes per day (CPD), 15% in women who smoke 10-19 CPD, and 5% in women who smoke >20 CPD (32). Second, they are less effective at mitigating nicotine abstinence effects (e.g., craving/withdrawal) than pharmacotherapy (e.g., bupropion; ref. 33). Pregnant women report that nicotine withdrawal symptoms and craving are major reasons for their inability to quit smoking (34). Third, behavioral interventions are generally less efficacious than pharmacotherapy in treating ND in depressed smokers (33). Upwards of 12% of pregnant women have depression (1) and upwards of 50% of depressed pregnant women smoke (8). African American pregnant smokers with elevated depression symptom scores were half as likely as women with lower depression scores (17) to consider seriously quitting smoking during pregnancy. Fourth, women with low annual incomes are half as likely as those with higher

CONFIDENTIAL

This material is the property of the University of Pennsylvania. Do not disclose or use except as authorized in writing by the study sponsor

incomes to quit smoking during pregnancy (35), with behavioral interventions of particularly low efficacy in lower SES women (36, 37). Finally, women—especially pregnant women—are faster metabolizers of nicotine (13), making them less likely to respond to behavioral smoking cessation interventions and more likely to respond to pharmacotherapy (i.e., bupropion; ref. 15).

The utility of a smoking cessation treatment in pregnant women depends on its efficacy in smokers with greater severity of ND, craving and withdrawal, a high rate of co-morbid depression, more rapid nicotine metabolism, and economic disadvantage, which characterize many pregnant smokers (38).

**Pharmacologic Interventions for Smoking.** Several medications are FDA approved for smoking cessation in non-pregnant smokers. Nicotine replacement therapies (NRTs) partially replace the nicotine usually derived from smoking, relieving craving and other withdrawal symptoms (39, 40). The odds ratio (OR) of abstinence with NRTs compared to placebo varies from 1.5 for the nicotine gum to 2.3 for the nasal spray (12). Bupropion, a non-nicotine medication first approved by the FDA as an antidepressant, inhibits the neuronal reuptake of dopamine and norepinephrine (41). It has an OR of 2.1 for smoking cessation (12) and has been shown to reduce depressive symptoms in smokers (42), particularly smokers with high baseline depression (52). Varenicline, an  $\alpha 4\beta 2$  nicotinic receptor partial agonist (44), has an OR of 3.1 in promoting smoking cessation (12). However, there are no safety data on the use of varenicline for pregnant smokers. As discussed below, bupropion may be especially efficacious for smoking cessation in pregnant women.

**Studies of NRT for Smoking Cessation during Pregnancy:** In an effectiveness study (45), pregnant smokers received cognitive-behavioral therapy (CBT) and were randomly assigned to receive a choice of NRT (gum, patch, or lozenge) or no medication. Although the quit rate in the NRT group was approximately double that of the comparison group, the study was stopped because the NRT group had twice the serious adverse event (SAE) rate of the no-medication group. After adjusting for a history of preterm delivery, which was the most common SAE, the difference in SAE rate between groups was not statistically significant ( $p=0.09$ ). Three efficacy studies of NRT have been conducted in pregnant smokers (46-48). In a Danish study (46), all women received counseling and either 6 weeks of a nicotine patch or placebo. At the end of pregnancy, neither quit rates nor mean CPD differed by group. However, patch compliance was poor (i.e., the average use being only 2 weeks). In a US study (47), 194 pregnant smokers were randomly assigned to receive treatment with 2 mg gum or placebo combined with individual behavioral counseling. Smoking cessation rates were non-significantly higher in the NRT group. Importantly, despite limited adherence to NRT, it produced a greater reduction in CPD and cotinine concentrations than placebo and was associated with better treatment retention. Mean (SD) birth weight [3287 g (SD=569) vs. 2950 g (SD=657);  $p<0.001$ ] and mean gestational age [38.9 weeks (SD=1.7) vs. 38.0 weeks (SD=3.3);  $p=0.014$ ] were significantly greater in the nicotine group. In a UK study (48), 1,050 pregnant smokers were randomly assigned to nicotine patch or placebo for 8 weeks, combined with behavioral counseling. Although the quit rate was higher at 1 month in the NRT group (21.3% vs. 11.7% for placebo), the rate of abstinence from the quit date until delivery did not differ significantly (9.4% for NRT and 7.6% for placebo). Importantly, however, adherence was very low. Thus, NRT does not enhance quit rates in pregnant women, possibly due to the higher rate of metabolism (i.e., inactivation) of nicotine in pregnancy and poor medication adherence in the studies.

**Rationale for the Choice of Bupropion for Smoking Cessation During Pregnancy:** To date, there are no published studies of bupropion SR for smoking cessation during pregnancy (49). There are several reasons to evaluate bupropion in the treatment of pregnant smokers. First, pregnancy increases the rate of nicotine metabolism (13), which diminishes

CONFIDENTIAL

responsiveness to behavioral interventions and NRT (14, 15). Bupropion, by contrast, is efficacious for smoking cessation in fast metabolizers of nicotine (15). Second, although precise statistics are not yet available on the frequency with which bupropion is prescribed to pregnant women, it was the fourth most commonly prescribed antidepressant in pregnancy in 2007 (16). Moreover, bupropion in combination with cognitive behavioral therapy appears to promote greater smoking cessation rates and a longer time to relapse than placebo among women with smoking-related weight concerns (50), a potential contributing factor to smoking and relapse in postpartum smokers, including lower SES women (51). Further, depressive symptoms are common in pregnant women and are linked to continued smoking and data suggest that depressed smokers may respond better to bupropion than non-depressed smokers (52). Finally, bupropion appears to be safer than NRT for use in pregnancy. De Long et al. (53) examined the effect of fetal and neonatal exposure to bupropion on postnatal metabolic and reproductive outcomes in rats. In contrast to fetal exposure to nicotine (54), exposure to bupropion did not adversely affect metabolic outcomes or the fertility of the female offspring. Lastly, a small, preliminary study (55) showed that bupropion reduced CPD and improved mood among pregnant smokers more than citalopram/escitalopram.

In summary, behavioral interventions for smoking cessation in pregnant women are of limited efficacy, failing to adequately address several factors that are particularly relevant to smoking in this population (e.g., depression, rate of nicotine metabolism). Of the first-line medications, NRT has shown limited efficacy in pregnant smokers and in animal models of fetal exposure is associated with a number of potential adverse effects on offspring. Although varenicline is efficacious in non-pregnant smokers, there is an absence of safety data on its use in pregnancy. Bupropion is efficacious in non-pregnant smokers, is less likely to cause adverse fetal effects than nicotine, and is efficacious in fast metabolizers of nicotine and smokers with depressive symptoms and weight concerns (all factors that are common during pregnancy). Thus, we propose to conduct the first adequately powered RCT of bupropion to treat ND in women who continue to smoke during the second trimester of pregnancy.

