### 5.3. Method for Assigning Participants to Treatment Groups

Participants will be randomly assigned to one of two treatment conditions: Bupropion 300 mg/day (n = 180) or placebo (n = 180). We will use small-block randomization by site (Penn or MATER) provided by [name], the study biostatistician. A PHQ-9 score of 10 or greater will be used to identify major depression and stratify the randomization on it. Study site (Penn or MATER) will be the second of the two stratification variables. Study staff and the Investigational Drug Service (IDS) staff will be responsible for medication randomization. The process for randomization is: 1) The research coordinator will complete a “randomization form,” which includes the variables to be entered into the randomization program and fax or email the form without protected health information to the UPenn site; 2) A designated study staff member

Table 1: Medication Dispensing Schedule

	Medication Dispensed For	Morning Dose	Evening Dose	Total Daily Dose
Visit A: Screening	N/A	No medication	No medication	
Visit B: Baseline	Wk 1	150 mg	No medication (for first 3 days); then 150 mg	150 mg
Visit C: Wk 1	Wk 2 through Wk 5	150 mg	150 mg	300 mg
Visit D: Wk 3	N/A	N/A	N/A	N/A
Visit E: Wk 5	Wk 6 through Wk 10	150 mg	150 mg	300 mg
Visit F: Wk 7		150 mg	150 mg	300 mg
Visit G: Wk 10	Endpoint	No medication	No medication	N/A

CONFIDENTIAL

This material is the property of the University of Pennsylvania. Do not disclose or use except as authorized in writing by the study sponsor

Visit H: Wk 24 Post-TQD	N/A	No medication	No medication	N/A
Visit I: 2 wk postpartum	N/A	No medication	No medication	N/A
Visit J: 6 wk postpartum	N/A	No medication	No medication	N/A

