## 7. Statistical Plan

### 7.1. Power

A power analysis is provided only for the primary aims because the exploratory aim is hypothesis generating. Most of our power calculations were approximated as 2-sided t- or z-tests, with  $\alpha = 0.05$ , using PASS Software (Power and Sample Size, NCSS Software, Kaysville, UT). Equivalence testing was approximated as two one-sided tests, with  $\alpha = 0.025$  each.

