**H2:** We will compare treatment arms for equivalence of the frequency of moderate-to-severe AEs (individual and total). The hypothesis test for equivalence is a test of whether the OR is out of the prescribed range for the difference between the treatment arms. Using logistic regression, we will conduct two one-sided tests against predefined upper and lower equivalence boundaries on percent reporting only mild AEs. The test-statistic will be the z-score corresponding to the log of the OR. This provides a more valid test of the potential safety of bupropion for pregnant smokers than a simple comparison of mean responses on a measure of AEs.

**H3:** Mean birth weight will be compared for treatment groups using a two-sample t-test, in the context of multiple linear regression. The regression format allows us to add covariates to adjust for imbalances in participant characteristics between treatment arms. Treatment will be entered as a binary indicator. In a secondary analysis, we will also compare the percentage of participants in each group that delivers an infant of LBW (1500-2500 g) or preterm delivery. These secondary hypotheses will be tested using the z-score corresponding to the OR that will be estimated using logistic regression.

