### **8.4 Unblinding Procedures**

In the event that participants are prematurely discontinued, it will be necessary to avoid breaking the blind whenever possible, in order to protect the integrity of the study. If an emergency necessitates that the blind be broken, only the pharmacist will have access to the unblinding codes and will be given the names of the staff with authority to request that the blind be broken. If the IDS or hospital pharmacy is contacted by other persons in requesting the study blind be broken for a participant, and the study physician is not reachable, the pharmacist will act according to his/her best judgment in deciding whether or not to break the study blind for that participant. The hospital pharmacist can be reached 24 hours a day by beeper to rapidly access participant unblinding codes.

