## **SAFETY MONITORING AND REPORTING PROTOCOL**

**Adverse Event Determination and Reporting Procedures.** For this study, we will use established Penn procedures and infrastructure for data and safety monitoring and a protocol-specific Data and Safety Monitoring Board (DSMB). The specific elements of our plan is as follows: 1) all project staff will complete certification in the protection of research participants; 2) the protocol will be submitted for review to the IRB and all procedures and policies outlined by the IRB will be followed for this study; and 3) a DSMB will be established to review the progress of accrual and the safety of participants. We will supply the designated IRB with ongoing progress reports for the study and a formal review of the study will be conducted annually or more frequently as designated by the IRB. The Penn IRB will act as the IRB of record for both sites per the IRB Authorization Agreement signed by both sites. The City of Philadelphia IRB will receive an annual report and be informed of all SAEs and reportable events. The IRB may suspend, terminate or restrict the study as appropriate. Each participating investigator must complete certification in the protection of research participants. Finally, [name] (at Penn) and [name] (MATER/Jefferson) will manage the flow of documents to external agencies to facilitate ongoing and timely review. The IRB will audit the study as needed and will review all data on a regular basis at least every 12 months. All serious adverse events (SAEs) will be reviewed on a real-time basis first by the study physicians. An existing protocol for adverse event monitoring and adverse event reporting will be used (see below). The DSMB will consist of four individuals who are not involved in the study: a statistician ([name]., Assistant Professor of Medical Science at Quinnipiac University), an obstetrician ([name]., Associate Professor of Obstetrics and Gynecology at Penn), a clinical trialist ([name]., Professor of Psychiatry at Penn) and a women's behavioral wellness specialist ([name], Professor of Psychiatry and Ob/Gyn at Penn). The DSMB will establish guidelines for adverse event reporting. The DSMB will meet annually, with additional meetings, as may be required. Prior to meetings, all members of the DSMB will receive a report describing study progress, including enrollment, treatment completion or early termination, and a summary of all adverse events. A formal data and safety monitoring plan, detailing the DSMB's activities, will be submitted to the IRB for review and approval prior to study initiation and periodic reports will be included with annual IRB reviews.

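### H2 judges safety on symptom severity and compares no overall serious adverse event rate by arm, and the DSMB report is not specified by arm

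*Combined protocol and SAP*

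**What the plan says.** **Final analysis.** The Study Summary states: "We will also compare treatment arms for equivalence of the frequency of moderate-to-severe adverse events (individual and total". For H2, section 7.2.2 runs two one-sided tests against "upper and lower equivalence boundaries on percent reporting only mild AEs". Section 2 words H2 in terms of severe treatment-related AEs, and section 3.2 in terms of moderate or severe side effects. All of these are severity grades. Section 10.1 defines severity by interference with daily activities; section 8.1 defines seriousness separately (fatal, life-threatening, hospital stay, disability and, for the neonate, congenital anomaly). Section 3.4, titled Safety Endpoints, holds a withdrawal rule and no endpoint.

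**Obstetric and birth outcomes.** Section 7.1.1 places Apgar scores, birth weight, duration of pregnancy, obstetrical complications and NICU admission inside the H2 safety analyses. Section 7.2.2 compares low birth weight and preterm delivery by arm using logistic regression.

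**During the trial.** Section 10.1 says that DSMB members receive "a report describing study progress, including enrollment, treatment completion or early termination, and a summary of all adverse events". It does not say whether this is by arm. The monitoring plan in the Appendix gives the board a remit over safety, conduct and efficacy, and lets it recommend termination.

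**Background.** Section 1.1 describes an NRT trial in pregnancy where "the study was stopped because the NRT group had twice the serious adverse event (SAE) rate of the no-medication group". It continues: "After adjusting for a history of preterm delivery, which was the most common SAE", the difference was no longer significant (p=0.09).

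**The concern.** The H2 measure is dominated by common symptoms. Section 7.1.1 expects 45% of women on bupropion and 47% on placebo to have no moderate-to-severe AE, so 55% and 53% count as events. A woman with moderate dry mouth and a woman with a seizure each count once. A shift in rare, grave events can therefore be lost in the total, and H2 could be read as showing safety while SAEs were more frequent on bupropion.

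The birth-outcome comparisons cover part of the gap. They do not cover the overall SAE rate, or fetal or neonatal death and congenital anomaly. Nor do they cover maternal seizure or antepartum hospitalization as serious events. They also come after enrolment has ended. If the DSMB table were not split by arm, the board could not see an imbalance while women were still entering.

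**Working it through.** **Inputs.** Allocation is "Bupropion 300 mg/day (n = 180) or placebo (n = 180" (section 5.3). Section 7.1 says: "Most of our power calculations were approximated as 2-sided t- or z-tests, with" alpha 0.05; equivalence uses two one-sided tests at 0.025 each. The H2 window is 0.30 to 0.60 (section 7.1.1). No placebo SAE rate is given, so 5%, 10% and 15% are assumed.

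**1. Check of the formula on the plan's own figure.** Power = Φ[(|p2 − p1| − 1.96·SE0)/SE1], with SE0 = √(2·p̄(1 − p̄)/n) and SE1 = √((p1(1 − p1) + p2(1 − p2))/n). For H1, p1 = 0.212, p2 = 0.359, n = 180, p̄ = 0.2855:

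- SE0 = 0.0476 and SE1 = 0.0470
- (0.147 − 0.0933)/0.0470 = 1.14, so power = 87.3%, against 88% stated (87.9% with unpooled variance). It reproduces.

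**2. The same formula for a doubled SAE rate.** The interval is the risk difference ± 1.96·SE1 at the assumed rates.

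| Placebo vs bupropion | Power, 180 per arm | Fisher exact | Power, 90 per arm | Expected difference (95% CI), 180 per arm |
|---|---|---|---|---|
| 5% vs 10% | 44% | 36% | 25% | 5 points (−0.4 to 10.4) |
| 10% vs 20% | 76% | 72% | 47% | 10 points (2.7 to 17.3) |
| 15% vs 30% | 93% | 92% | 68% | 15 points (6.5 to 23.5) |

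Eighty per cent power needs a placebo rate of about 11%.

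**3. Would H2 react to a doubling?** Assume that 45% of each arm would otherwise be free of moderate-to-severe AEs, that every SAE counts as one, and that SAEs are independent of other AEs. With SAEs at 10% and 20%, the AE-free share on bupropion becomes 0.45 × 0.80/0.90 = 0.40, inside the window. The margins are ±0.15 around 0.45:

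- SE = √((0.45·0.55 + 0.40·0.60)/180) = 0.0520
- Lower bound: Φ[(−0.05 + 0.15)/0.0520 − 1.96] = 0.485
- Upper bound: Φ[(0.15 + 0.05)/0.0520 − 1.96] = 0.970
- Both bounds met: 0.485 + 0.970 − 1 = 45%. On the log-odds scale that section 7.2.2 uses, it is 51%. Simulation gives the same two values.

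With no SAE difference the same calculation gives 63% and 68%. A doubling of SAEs thus lowers the chance of declaring equivalence by only about 17 to 18 points. For 5% to 10% the share is 0.426 and the chance is 59% to 65%; for 15% to 30% it is 0.371 and 27% to 31%. (The plan's 82% for H2 is not reached by the joint test. That is a separate matter.)

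**4. SAE window.** Section 10.1 sets SAE reporting from the first dose to 28 days after stopping drug. Section 8.1 runs AE reporting to the last assessment. Entry is at 13 to 26 weeks with 10 weeks of drug, so the 28-day window closes at 13 + 10 + 4 = 27 to 26 + 10 + 4 = 40 weeks of gestation, or up to about 4 weeks later when baseline follows screening by the permitted 30 days. For a woman starting drug before 23 weeks it closes before 37 weeks (23 + 10 + 4 = 37), the preterm limit.

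**5. DSMB frequency.** Section 8.5 says twice a year; section 10.1 says annually, with extra meetings as required.

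**The case against.** A reader might infer that the cited trial's signal would go unseen here. The documents do not support that for the end of the trial. Preterm delivery was the commonest SAE in that trial, and this plan compares it by arm and claims over 89% power for it (section 7.1.1). NICU admission, itself a neonatal SAE criterion apart from neonatal abstinence syndrome, and obstetrical complications are also named. Seizure is on the AE checklist, so the individual-item comparisons might list it. This part of the objection stands and narrows the point. It does not close the gap: section 7.1.1 gives no equivalence margin for NICU admission or complications, section 7.2.2 gives them no model, and none of these is a count of women or pregnancies with any SAE. History of preterm delivery is only an optional covariate, listed under H1.

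A reader might also infer that the DSMB sees pooled data only, because "only the pharmacist will have access to the unblinding codes". That does not follow. Section 8.4 concerns emergency unblinding, section 5.7 blinds participants and research staff, and section 5.3 has separate designated staff handling the assignments. None of this bars a closed report to members who are outside the study, and a remit that includes efficacy sits poorly with pooled data. Some pages next to the DSMB and monitoring text were not available for this review. Arm-level review is therefore unspecified, not ruled out.

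Real-time physician review and reporting to the IRB, NIH and FDA are genuine safeguards, but they deal with single cases. Nothing in the available text has them compare SAE counts by arm.

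**Conclusion.** The point holds in this limited form and should be acted on. H2 rests on a severity grade, and no available text compares SAEs by arm as a whole. Under the assumptions in step 3, H2 would still declare equivalence in roughly half of trials in which SAEs had doubled from 10% to 20%. If SAEs fell mainly in women who already report moderate symptoms, or were neonatal and so outside the maternal symptom count, H2 would react even less.

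It cannot be said that the design would reliably detect a doubling. Power runs from 44% to 93% over the assumed placebo rates and is lower at half enrolment. The estimate and its interval are what matter, and a non-significant result would not be reassuring. The cited trial is motivation only: its own difference had p=0.09 after adjustment, and describing it is not an error in the plan.

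**What to change.** - **Section 7.2.2, H2.** Add, by randomised arm, the proportion of women with any maternal SAE and the proportion of pregnancies with any fetal or neonatal SAE, each with a risk difference and 95% CI. Adjust for history of preterm delivery, using the pregnancy outcomes collected at baseline (section 6.3). State that H2 equivalence will not be read as evidence of safety if the SAE interval indicates harm, and that an interval including zero is not evidence of no difference.
- **Section 10.1.** State that the DSMB receives AEs and SAEs by masked arm (A/B) in a closed report, prepared apart from the blinded study team.
- **Reconcile.** Align the SAE window in section 10.1 with the AE window in section 8.1, so that the SAE analysis covers births. Align the DSMB meeting frequency in sections 8.5 and 10.1.

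The cost is wording in the SAP and DSMB plan, one by-arm table per meeting, and a small extra step to protect the blind. The maternal comparison uses data already collected. The neonatal comparison depends on settling the window, and may need SAE coding of delivery records that are already abstracted.
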